	
The treatment period includes the Baseline (Day 0) Dosing Visit day, and Major and Minor Dosing Visit days. Refer to Table 2, Table 3, Table 4, and Section 7.
 
Baseline (Day 0) Visit Day
 
In addition to the safety and tolerability assessments described above, the subject will be administered the study drug and the following procedures will be conducted: pregnancy test (if applicable), PDAI, PK, PD, and immunogenicity sample collection, photography of lesions, and serum tetanus and varicella zoster virus (VZV) antibody tests. An optional skin biopsy may be collected. HR-QoL is assessed in all cohorts except Cohort 1. A complete list of assessments is provided in Table 2, Table 3, Table 4, and Section 7.
 
Major Dosing Visit Days
 
In addition to the safety and tolerability assessments described above, the subject will be administered the study drug, and the following procedures will be conducted: PDAI, PD, and immunogenicity sample collection. A complete list of assessments is provided in Table 2, Table 3, Table 4, and Section 7.
 
Minor Dosing Visit Days
 
In addition to the safety and tolerability assessments described above, the subject will be administered the study drug, and the following procedures will be conducted: PDAI and PD sample collection. A complete list of assessments is provided in Table 2, Table 3, Table 4, and Section 7.
 
Follow-up Period/End of Study (84 days)
 
The follow-up period includes the Major and Minor Follow-up Visit days. Subjects are encouraged to participate in all visits up to and including Day 112 (Cohorts 1 and 2) or Day 175 (Cohort 3) to ensure study completion. Refer to Table 2, Table 3, Table 4, and Section 7.
 
Major Follow-up Visit Days
 
In addition to the safety and tolerability assessments described above, the following procedures will be conducted: PDAI, PD sample collection, photography of lesions and HR-QoL assessments. A complete list of assessments is provided in Table 2, Table 3, Table 4, and Section 7.
 
Minor Follow-up Visit Days
 
In addition to the safety and tolerability assessments described above, the following procedures will be conducted: PDAI and PD sample collection. A complete list of assessments is provided in Table 2, Table 3, Table 4, and Section 7.
 
Dosing for any individual subject will be discontinued (ie, further treatment with the study drug will not be given) if the subject experiences any study drug-related SAE or any study drug-related non-serious adverse event that, in the judgement of the Investigator (following consultation with the Medical Monitor, if desired) suggests that it could be unsafe to administer further study drug to that subject. Additionally, a subject will be discontinued from further treatment with study drug at the discretion of the Investigator, with consultation with the Medical Monitor if desired, if they require a significant increase in anti-pemphigus medications for the management of pemphigus.

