### Permitted Medications

Concomitant medication and treatment for co-existing conditions, including those for pemphigus, are permitted if not listed as prohibited.

1. Topical antibiotics to treat active infections that occur during the study.
2. Topical or systemic treatments for oral candidiasis.
3. Topical lidocaine for transient pain relief as needed.
4. Concomitant treatment that is medically indicated for any AEs the subject experiences during the study.
5. Medication for potential infusion reactions: The Investigator may recommend prophylactic use of acetaminophen, IV hydration, diphenhydramine, histamine2 (H2) blockers (eg, ranitidine, famotidine), etc to manage potential infusion reactions.
6. Low-strength corticosteroids (eg, hydrocortisone ≤1%) applied to a single lesion contributing <10% of the PDAI total activity score.
7. Topical tacrolimus, sirolimus or pimecrolimus applied to a single lesion contributing <10% of the PDAI total activity score.

8. Dexamethasone elixir solution for oral lesions if dose remains stable throughout trial participation (swish and spit only).
9. Stable regimen of the following systemic immunosuppressants: azathioprine, mycophenolate mofetil, methotrexate, dapsone, cyclosporine, tacrolimus, sirolimus, or low dose oral cyclophosphamide ( $\leq 100$  mg/day).

One month after the final dose of SYNT001, corticosteroids may be tapered at the Investigator's discretion.

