### **Prohibited Medications**

Use of the following medications will not be permitted during the study unless specified above as permitted:

1. Rituximab or other anti-CD20 antibody
2. Monoclonal antibodies other than study drug
3. Any topical or systemic immunosuppressive drugs apart from those that are listed as permitted.
4. IV corticosteroids prior to infusion (except in subjects who received corticosteroids for treatment of a prior infusion reaction to SYNT001)
5. Any dietary herbal supplements
6. Any investigational drug or device
7. Vaccinations within 2 weeks of screening through 28 days following final dose of study drug

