## 9. STUDY RULES

### 9.1 Subject Withdrawal

Every reasonable effort will be made to keep the subject in the study; however, if a subject withdraws from the study, the Investigator should complete and report the reasons for withdrawal as thoroughly as possible. The reason(s) for termination must be clearly documented on the appropriate page of the eCRF.

If a subject discontinues from the study for any reason, every effort will be made to collect all clinical and laboratory data as scheduled for the Early Termination Visit (see [Section 8.4](#)). If the subject fails to return for these assessments for unknown reasons, every effort (eg, telephone, email, and letter) should be made to contact them.

The reason(s) for a subject's participation in the study may be prematurely discontinued will be documented and include:

1. The subject wishes to withdraw from the study.
2. Request by a regulatory agency (eg, Institutional Review Board).
3. The subject experiences a significant or intolerable AE.
4. The subject experiences a significant adverse change in vital signs, physical examination findings, or clinical laboratory parameter.
5. The subject has a need for a concomitant medication that is not permitted by the study protocol.
6. The subject experiences generalized impairment or mental incompetence that would result in the subject being unable to understand his or her participation in the study.
7. If, in the Investigator's medical judgment, further participation would be injurious to the health and well-being of the subject, or is not in the best interest of the subject.
8. Administrative reasons, such as subject non-compliance or a major protocol violation.
9. The subject requires a significant increase in dose(s) of anti-pemphigus medication(s) for the management of pemphigus (at the discretion of the Investigator with consultation with the Medical Monitor).

If at the discretion of the Investigator with consultation with the Medical Monitor, a subject requires a significant increase in dose(s) of anti-pemphigus medication(s) for the management of pemphigus, the subject will be encouraged to continue their study visits to allow collection of safety data.

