### 10.2 Adverse Events

An AE is defined as any untoward medical occurrence in a clinical trial subject associated with the use of a drug, whether considered drug related or not. An AE can be an unfavorable and unintended sign (eg, an abnormal laboratory value finding), a symptom, or a disease temporally associated with the use of a drug, without judgment as to causality. An AE can arise from use of the drug (eg, use in combination with another drug) and from any route of administration, formulation or dose, including an overdose. An AE also includes, but is not limited to, any clinically significant worsening of a pre-existing condition. Examples include:

- Any sign, symptom, physical finding, or laboratory result that has worsened in nature, severity or frequency compared to baseline
- Reactions from an investigational drug, including those occurring because of an overdose, abuse of the study drug, withdrawal phenomena, sensitivity or toxicity
- Concurrent illness that was not present or worsens in nature, severity, or frequency compared to baseline
- Injury or accident
- Exacerbation of a pre-existing condition

Pregnancy is not considered an AE or SAE; however, any pregnancy complication(s) should be recorded as an AE(s) or SAE(s) (if applicable). Elective abortions without complications should not be regarded as AEs, unless they were therapeutic abortions. Hospitalization for normal delivery of a healthy newborn should not be considered an SAE. If a female subject becomes pregnant during the conduct of the study, the Investigator must notify the Sponsor according to the procedures provided in [Section 10.5.4](#).

Planned hospitalization admissions or surgical procedures for a condition known to exist before the subject signed the informed consent are not an AE and should be recorded as medical history. If the planned hospitalization or procedure is executed as planned and without complication, the record in the subject's medical history is considered complete. However, if the event/condition deteriorates in an unexpected manner during the study or following surgery, it must be reported as an AE according to the procedures provided in [Section 10.2.1](#).

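### The protocol's rules for treating a pemphigus flare are inconsistent and its PDAI response criterion sets no condition on rescue, so a rescued subject can be counted as a responder to the assigned dose

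*Protocol*

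**What the plan says.** Five parts of the protocol bear on a subject whose pemphigus worsens.

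- **Adverse event definition (Section 10.2).** "An AE also includes, but is not limited to, any clinically significant worsening of a pre-existing condition", and the listed examples include "Exacerbation of a pre-existing condition". Pemphigus, the disease under study, is not excepted.
- **Permitted medications (Section 7.12, repeated in the Synopsis).** Treatments for co-existing conditions, "including those for pemphigus, are permitted if not listed as prohibited". Item 4 adds "Concomitant treatment that is medically indicated for any AEs the subject experiences during the study", with no limit on drug class or dose.
- **Prohibited medications (Section 7.12, repeated in the Synopsis).** The list, which includes anti-CD20 antibodies, other monoclonal antibodies and immunosuppressants not listed as permitted, opens with "Use of the following medications will not be permitted during the study unless specified above as permitted".
- **Consequences.** Under Study methodology in the Synopsis, "a subject will be discontinued from further treatment with study drug at the discretion of the Investigator" if a significant increase in anti-pemphigus medication is needed. Section 9.1 gives as reasons for ending participation the need for a drug that is not permitted (item 5) and "The subject requires a significant increase in dose(s) of anti-pemphigus medication(s) for the management of pemphigus" (item 9). Its closing paragraph says that in the item 9 case "the subject will be encouraged to continue their study visits to allow collection of safety data". No passage defines a significant increase.
- **Response criterion (Sections 3.4 and 11.4.3.2).** Dose selection uses a reduction of at least 50% from baseline in PDAI total activity score. Section 3.1 describes this as a proportion of responders. No condition on rescue is stated.

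**The concern.** Effective rescue lowers PDAI. If a subject whom SYNT001 has not helped is rescued, stays in follow-up and then shows a 50% fall, the criterion as written is met. The subject then counts towards the dose that failed. Dose selection is a primary objective and is to be read from descriptive proportions in very small open-label cohorts, so a single subject matters.

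The inconsistent site instructions add to this. They leave unclear which agents may be given for a flare, and whether the result is a stop of study drug, the end of participation or neither. That determines who receives rescue and still contributes PDAI scores.

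**Working it through.** The protocol states no figure to reproduce here; Section 11.3 says that no formal sample size calculation was done. The check is a reading of the passages followed by simple counts.

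**Following a flare through the text**

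1. A clinically significant flare is an adverse event under Section 10.2.
2. Item 4 permits treatment that is medically indicated for it.
3. Suppose the indicated agent is on the prohibited list. The permitted list's lead-in says pemphigus treatment is allowed only if it is not prohibited. The prohibited list's lead-in says the ban holds only if the agent is not permitted above. Each defers to the other. One available reading lets item 4 lift the ban; another leaves the ban in place and brings item 5 of Section 9.1 into play.
4. Suppose instead that an existing anti-pemphigus drug is increased. If the increase is judged significant, the Synopsis stops study drug and item 9 lists it as a reason to end participation, while the closing paragraph of Section 9.1 encourages continued visits. If it is not judged significant, neither provision is triggered. The threshold is left to discretion.
5. Sections 6.1 and 9.2 follow subjects who miss doses through all scheduled visits, and PDAI is on the schedule (Tables 2 to 4).
6. Sections 3.4 and 11.4.3.2 apply the 50% criterion without reference to any of this.

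**PDAI visits still to come after a rescue at Day 14 (example day)**

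- Cohort 2 (Table 3): Days 21, 28, 35, 42, 56, 84, 112 = 7 visits.
- Cohort 3 (Table 4): Days 21, 28, 35, 42, 49, 56, 63, 70, 77, 84, 91 (11 visits) plus Days 98, 105, 119, 147, 175 (5 visits) = 16 visits.

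**Effect of one subject on the response proportion**

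Shift = 1/n. Cohorts 2 to 4 have 4 subjects, extendable to 8; Cohort 1 has up to 8.

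- n = 4: 1/4 = 25 percentage points, for example 2/4 = 50% becoming 3/4 = 75%.
- n = 8: 1/8 = 12.5 percentage points.

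**Chance that a cohort contains at least one rescued subject**

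The documents give no rescue rate, so p is an assumption, shown over a range. Formula: 1 − (1 − p)^n.

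| Assumed p | n = 4 | n = 8 |
|---|---|---|
| 10% | 1 − 0.9^4 = 34% | 1 − 0.9^8 = 57% |
| 20% | 1 − 0.8^4 = 59% | 1 − 0.8^8 = 83% |
| 30% | 1 − 0.7^4 = 76% | 1 − 0.7^8 = 94% |

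These are chances of a rescue occurring, not of a false response. A false response also needs the 50% fall to be reached after the rescue and the subject to be counted.

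**The case against.** The best defence is that the passages mostly fit together and the rest belongs to the SAP. Several stronger readings are tempting, and the documents do not support them.

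- **That item 4 simply overrides the prohibited list.** Item 4 names no medication, is confined to treatment that is medically indicated, and sits beside items 6 to 9, which do name agents and set limits. Anti-CD20 antibodies are prohibited by name. A site could reasonably hold that the ban stands. The override is a possible reading and not the settled meaning; what stands is that the circular lead-ins do not decide between the two.
- **That recording the flare as an adverse event avoids the stopping provisions.** It does not. The Synopsis rule and item 9 are triggered by the increase in medication, whatever the event is called. What stands is that the size of increase that triggers them is undefined.
- **That stopping study drug and continuing visits contradict each other.** They do not; stopping treatment while following the subject is coherent, and Section 9.1 lists reasons for which participation may be ended, not must be.
- **That rescued subjects will be counted as responders.** The protocol does not say so. Section 9.1 gives safety data as the purpose of continued visits, Section 11.4.1 leaves detailed methods to the SAP, and the SAP, which is not shown, could class these subjects as non-responders. Rescue would also be visible, because all treatments are recorded and corticosteroid use is summarised.

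The last point limits the finding but does not remove it. The SAP can settle how a score is counted. It cannot settle conflicting instructions to sites on what may be given and who remains under follow-up. The protocol itself states the primary response criterion in two places, without condition.

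**Conclusion.** The point holds in a limited form. The protocol gives no single status or consequence for treating worsening pemphigus: the adverse event definition, permitted item 4, the two list lead-ins, the Synopsis stopping rule and Section 9.1 have to be reconciled. Because the PDAI criterion sets no condition on rescue, following the text can credit rescue to a SYNT001 dose.

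Each subject so counted is worth 25 points at n = 4 and 12.5 points at n = 8. That is the effect per subject, not an expected bias, since the rescue rate and the response to rescue are not in the documents. The conclusion rests on the protocol text alone and assumes no SAP rule to the contrary. It takes no position on which treatment or stopping rule is right.

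**What to change.** 1. Reconcile the Synopsis (Study methodology, and Permitted and prohibited concomitant treatments), Section 7.12 and Section 9.1 so that treatment of worsening pemphigus has one stated status and one stated consequence throughout. This includes making clear which list governs when both apply and what counts as a significant increase. The choice of clinical rule is for the sponsor.
2. In Sections 3.4 and 11.4.3.2, state that a subject whose 50% PDAI fall is first reached after a start or increase of anti-pemphigus medication counts as a non-responder for dose selection, however the event was recorded.
3. In Section 11.4.4.4, flag PDAI values after that change in the by-visit summaries, so that they remain visible but are not read as the effect of SYNT001 alone.

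The cost is wording. The medication records needed are already collected under Section 7.12. The drawback is that the reported response proportion may be slightly lower, since a subject who would have responded without the added medication is also counted as a non-responder.

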### **Prohibited Medications**

Use of the following medications will not be permitted during the study unless specified above as permitted:

1. Rituximab or other anti-CD20 antibody
2. Monoclonal antibodies other than study drug
3. Any topical or systemic immunosuppressive drugs apart from those that are listed as permitted.
4. IV corticosteroids prior to infusion (except in subjects who received corticosteroids for treatment of a prior infusion reaction to SYNT001)
5. Any dietary herbal supplements
6. Any investigational drug or device
7. Vaccinations within 2 weeks of screening through 28 days following final dose of study drug

### **7.13 Skin Biopsy**

Optional skin biopsy samples from lesional or non-lesional skin will be collected to analyze SYNT001 levels.

## 8. STUDY ASSESSMENTS

Study assessments are performed on a weekly basis and will be comprised of the following periods: Screening, Treatment (including Baseline [Day 0]), and Follow-Up (including End-Of Study). For those subjects that complete all periods in Cohorts 1 and 2, study duration is 112 days. For those subjects that complete all periods in Cohort 3, study duration is 175 days.

Further detail on specific study assessments is provided in [Section 7](#).

### 8.1 All Cohorts: Screening Period and First Treatment (Day 0)

#### 8.1.1 All Cohorts: Screening Period (Day -14 to Day -1)

For all cohorts, informed consent must be obtained before any study-specific samples are taken or study-specific tests or evaluations are conducted. The following assessments at the screening visit are to occur within 14 days before dosing. Study eligibility will be based on satisfying all the study inclusion and exclusion criteria (see [Section 6](#)).

At the screening visit, information will be collected and subjects will have clinical evaluations as follows:

- Informed consent
- Medical history and demographic data
- Review inclusion and exclusion criteria
- Complete physical examination, including height and weight
- Vital sign measurements (after 5 minutes of rest; sitting blood pressure, heart rate, respiratory rate, oral temperature); abnormal results to be repeated after 5 minutes of rest
- Clinical safety laboratory tests (hematology, serum chemistry panel, urinalysis)
- Pregnancy test
- Hepatitis and HIV screen
- 12-lead ECG (to be obtained in triplicate after 5 minutes of rest in the supine position)
- PD sample collection
  - IgG, IgG subtypes (IgG1-4), IgA, IgM
  - Anti-Dsg1 and Dsg3 antibody titers
- Concomitant medication assessment
- AE assessment

#### 8.1.2 All Cohorts: Enrollment and First Treatment (Day 0)

For all cohorts, study Day 0 is defined as the date the subject is administered their first dose of study drug. On Day 0, subjects will be asked to come to the clinic and the following procedures will be performed prior to the first dose of study drug:

- Complete physical exam
- Vital sign measurements (sitting blood pressure, heart rate, respiratory rate, oral temperature) and pulse oximetry; to be measured immediately prior to the infusion

- Clinical safety laboratory tests (hematology, serum chemistry panel, urinalysis)
- Pregnancy test
- Serum tetanus antibody and VZV antibody
- PDAI
- PK baseline sample collection (collected just prior to the start of the study drug infusion)
- Immunogenicity sample collection (collected just prior to the start of study drug infusion)
- PD sample collection (collected just prior to the start of the study drug infusion)
  - IgG, IgG subtypes (IgG1-4), IgA, IgM
  - CIC
  - Anti-Dsg (1 and 3) antibody titers
  - C3
  - AECA
  - *FCGR2A* SNP via buccal swab
  - RNAseq
  - Urine IgG
  - Immunophenotyping
  - Exploratory pemphigus immune response biomarkers
- Skin biopsy (optional) (*Cohort 1 only*)
- Photography
- HR-QoL assessments (ABQoL, Skindex-29) (*Cohorts 2 and 3 only*)

**After the preceding procedures and assessments are completed:**

- Study drug administration (record date and time of dose of study drug)
- Vital sign measurements (sitting blood pressure, heart rate, respiratory rate, oral temperature) and pulse oximetry will be performed at 15, 30, and 45 minutes after the start of the infusion and at completion of the infusion

**After administration of study drug, the following post treatment procedures and assessments will be performed:**

- Vital sign measurements (sitting blood pressure, heart rate, respiratory rate, oral temperature) and pulse oximetry: 30 minutes, 1 hour, and 2 hours following completion of the infusion; abnormal results to be repeated after 5 minutes of rest
- PK sample collection at 5 minutes. Thereafter at 2, 4, 6 hours (Cohort 1) or 1 and 2 hours (Cohorts 2 and 3) after the completion of study drug infusion; record collection date and time for each PK sample
- 12-lead ECG (to be obtained in triplicate at 5 minutes after the completion of study drug infusion)

**Throughout the study visit, the following assessments will be performed:**

- Concomitant medication assessment
- AE assessment

## **8.2 Cohort 1: Day 1 to 84**

### **8.2.1 Cohort 1: Follow-up Day 1**

On Day 1 (24 hours  $\pm$  1 hour from end-of-infusion time on Day 0), the subject will return to the clinic and the following procedures are to be performed:

- Vital sign measurements (after 5 minutes of rest; sitting blood pressure, heart rate, respiratory rate, oral temperature): abnormal results to be repeated after 5 minutes of rest
- PK sample collection (record collection date and time)
- PD sample collection
  - IgG, IgG subtypes (IgG1-4), IgA, IgM
- Skin biopsy (optional)
- Concomitant medication assessment
- AE assessment

